4.2 Efficacy Variables

- Urinary GAG Excretion: First morning void urine will be evaluated for uGAG concentration
- Biomarkers of inflammation in serum: Blood samples will be collected to evaluate levels of biomarkers of inflammation and response to treatment.
- Six Minute Walk Test (6MWT): The total distance walked (meters) in a six minute period
- Bruininks-Oseretsky Test of Motor Proficiency (BOT-2): This test of motor proficiency will be administered to evaluate treatment-related changes in four domains assessing both fine and gross motor function: fine motor precision, manual dexterity, balance, running speed and agility. The test may be modified and tests omitted to accommodate the needs of the subject.
- Three Minute Stair Climb Test (3MSCT): The number of stairs climbed within a three minute period.
- Pulmonary function testing: Spirometry will be administered to subjects who do not require invasive ventilatory support or have a tracheostomy. Pulmonary function variables include forced vital capacity (FVC) and maximum voluntary ventilation (MVV).
- Shoulder flexion maximum range of motion: Goniometry will be used to measure (in degrees) the maximum passive shoulder range of motion in both flexion and extension.

- Growth (anthropometric): Growth will be assessed by anthropometric measurements including standing height (or recumbent length or sitting height if applicable) and weight.
- Visual acuity: will be measured using a standard eye chart and recorded for each eye independently.
- Multi-domain Responder Analysis (MDRI): The multi-domain responder analysis will consider the scoring as described in Section 5.3.
- Individualized Clinical Response (ICR): Will only be assessed for subjects previously enrolling from the Ultragenyx-sponsored MPS 7 Phase 3 clinical study UX003-CL301 where an outcome of interest was previously selected from the possible clinical outcome measures, the same ICR identified in the feeder study may continue to be followed in this study.
- Scoring of Impactful Clinical Problems: The three most impactful clinical problems as reported by the subject/parent/caregiver during the Clinical Problem Evaluation will be scored on a Likert scale. For UX003 treatment-naïve subjects, the initial Clinical Problem Evaluation will occur at the Baseline visit. For subjects enrolling from the Ultragenyx-sponsored MPS 7 Phase 3 clinical study UX003-CL301, the Clinical Problems identified during the UX003-CL301 Randomization visit will continue to be scored throughout this study.
- Subject-reported disability, health related quality of life, and fatigue: The MPS Health Assessment Questionnaire, Childhood Health Assessment Questionnaire (CHAQ), or Health Assessment Questionnaire (HAQ) will be administered to evaluate treatmentrelated changes in self-care and mobility activities of daily living. The age-appropriate Pediatric Quality of Life Multidimensional Fatigue Scale (Peds QL-Multidimensional Fatigue Scale) will be administered to evaluate treatment-related changes in fatigue.
- Subject/Parent/Caregiver Clinical Global Impression (CGI) scales: Subjects or parents/caregivers will provide a global assessment of change using a CGI scale. In addition, subjects or parents/caregivers will provide narratives of their perception of how treatment has impacted the subject's ability to complete activities of daily living.
- Hepatosplenomegaly: Liver and spleen measurements will be assessed by physical exam.
- Cardiac ventricular mass/function: Ventricular mass will be assessed by echocardiogram (ECHO) and scored as a z-score relative to normal ventricular mass.

5 DEFINITIONS

5.1 Baseline

Naïve subjects:

• uGAG baseline is defined as the average of all assessments prior to or on the date of the first dose of UX003 in this study. Baseline value for other endpoints is the last non-missing assessment prior to or on the date of the first dose of UX003 in this study.

IST subjects:

- uGAG baseline is the average of all assessments prior to or on the date of the initiation of the initial treatment with UX003.
- Baseline value for other endpoints is the last non-missing assessment prior to or on the date of first dose of UX003 in this study.

Rollover subjects:

- The baseline (efficacy and safety) defined in feeder study will be used for this study.
- 5.2 Fold increase in uGAG above upper normal limit

The fold increase in uGAG above upper limit of normal is the ratio of the uGAG value over the uGAG upper limit of normal. If the ratio is less than 1, then it is set 1.

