# 7.5.2.1 Medical History

For subjects continuing treatment from a previous Ultragenyx sponsored study, general medical history information obtained during the primary (or feeder) study (e.g., UX003-CL301) will carry over to this study. The general medical history includes subject demographics (date of birth, ethnicity, and sex) and a history of major medical illnesses, diagnoses, surgeries and confirmation of MPS 7 diagnosis. To ensure all medical histories are complete and current, any enrolling subject who had an early termination in the primary study will have any changes or new information since their discontinuation in the primary study recorded.

For subjects who are treatment naïve or who enroll from a non-Ultragenyx sponsored study, a complete medical history is to be completed prior to the Baseline visit, or at the Baseline visit prior to first study treatment, to ensure subject meets all eligibility criteria. General medical information includes subject demographics (date of birth, ethnicity, and sex) and a history of major medical illnesses, diagnoses, and surgeries. Growth history for height (or recumbent length) and weight will be collected. MPS 7 treatment history and relevant concomitant medications will be recorded (start date, stop date, dose, dose regimen). Medications include prescription, over-the-counter, herbal and nutritional supplements. Any relevant concomitant therapy, including physical/occupational therapy will be recorded.

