#### 7.5.2.4 Vital Signs

Vital signs will include seated systolic blood pressure and diastolic blood pressure measured in millimeters of mercury (mm Hg), heart rate in beats per minute, respiration rate in breaths per minute, and temperature in degrees Celsius (°C). Vital signs measurements will be performed at every visit before any additional assessments are completed. On days when study drug will be administered, vital signs will be measured within 30 minutes before the infusion, at least every 30 minutes for the first hour of infusion, at least every hour for the remainder of the infusion, and within 30 minutes after the infusion. Additional measurements should be obtained as appropriate. Refer to the Study Reference Manual for additional details on vital sign assessments.

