# 7.6.6.3 Vital Signs

Vital signs will be summarized and listed by individual subject. Summaries of vital signs data over time and changes from Baseline over time will be provided.

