7.3 Visit Time Windows

Table 7.3.1 presents the visit window assigned for scheduled efficacy and safety assessments scheduled for every 12 weeks and the corresponding range of treatment days (window) during which an actual visit may occur.

Period	Visit	Scheduled Visit Day	Window			
First 48-Week Treatment Period	Baseline	Day 1	$Days \le 1$			
	Week 12	Day 85	Days [2, 127]			
	Week 24	Day 169	Days [128, 211]			
	Week 36	Day 253	Days [212, 295]			
	Week 48	Day 337	For subjects entered into continuation period Days [296, start of continuation period-1] For subjects did not enter into continuation period Days \geq 296			
Treatment Weeks 50-240	Week 60	Day 421	Days [start of continuation period, 463]			
	Every 12 Weeks	Day 84x ^a +421	[380+84x,463+84x]			
	Week 144	Day 1009	$Days \ge 968$			

Table 7.3.1:Visit Time Windows

a x=1,2...6

Termination visit for subjects who didn't complete the study, and unscheduled visits will be mapped to the closest post baseline scheduled visits if the scheduled visits are missing. If there are more than one unscheduled/end of study visits mapped to the same window, the one closer to the target day will be used. If more than one visit has the equal distance to the target day then the later one will be used, if more than one visits on the same day, use the time or the sequence number to select the later record. For listings and shift tables, all data points will be included.

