- j. For UX003 treatment-naïve subjects the three most impactful clinical problems reported by the subject/parent/caregiver will be identified and scored at the Baseline visit. These clinical problems will continue to be scored throughout this study. For subjects enrolling from the MPS 7 Phase 3 Ultragenyx sponsored study UX003-CL301, the three most impactful clinical problems reported by the subject/parent/caregiver during the UX003-CL301 randomization visit will continue to be scored throughout this study.
- k. Physical examinations are to include neurologic examination and evaluation of the presence or absence of corneal clouding. If subject complains of leg weakness or fatigue, evaluate for signs of cord compression (e.g., leg reflexes and motor strength).
- 1. On infusion days, vital signs will be measured at a minimum of: immediately (<30 minutes) before the infusion, at least every 30 minutes for the first hour of infusion, at least every hour for the remainder of the infusion and immediately (<30 minutes) after the infusion. Additional measurements should be obtained as appropriate.
- m. Laboratory samples (blood and urine) are to be collected prior to dosing of study drug. Clinical laboratory tests are to include hematology, chemistry, and urinalysis. Laboratory samples for safety performed within 30 days prior to Baseline may be used for the study baseline.
- n. For women of childbearing potential only. A serum pregnancy test will be performed in the event of a positive or equivocal urine pregnancy test result.
- o. Testing for IgG antibodies directed against rhGUS. Antibody sample must be collected before infusion.
- p. If a drug-related IAR has occurred, C3, C4 and CH50 samples should be drawn prior to and immediately after the next infusion.

- q. For subjects enrolling from an Ultragenyx-sponsored clinical trial, all AEs will be recorded from the time the subject signs the informed consent and completes the End of Treatment visit in the feeder study until 30 days after the last dose of study drug. For subjects who are treatment naïve or who are enrolling from a non-Ultragenyx-sponsored clinical trial, all AEs will be recorded from the time the subject signs the informed consent until 30 days after the last dose of study drug.
- r. Urine samples must be collected from first morning voids.

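### The SAP's date-only baseline rule makes the Day 1 vital-sign baseline a post-infusion reading for naïve and IST subjects

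*SAP*

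**What the plan says.** SAP 5.1 gives three baseline rules.

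- **Naïve subjects**, endpoints other than uGAG: the "last non-missing assessment prior to or on the date of the first dose of UX003 in this study".
- **IST subjects**, endpoints other than uGAG: almost word for word the same date-based rule, again tied to the first dose given in this study.
- **Rollover subjects**: "The baseline (efficacy and safety) defined in feeder study will be used for this study". This bullet also shows that the section is meant to cover safety data.

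No other part of the SAP gives a separate baseline for vital signs. SAP 8.8.3 says only that they will be summarised as appropriate.

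The first dose is given at the Baseline visit. Both schedules of events mark UX003 treatment and vital signs at Week 0, and Protocol 7.5.2.1 asks for the medical history of naïve and IST subjects before or "at the Baseline visit prior to first study treatment".

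On infusion days, Protocol 7.5.2.4 says "vital signs will be measured within 30 minutes before the infusion, at least every 30 minutes for the first hour of infusion". The vital-signs footnote to the SAP schedule continues: "at least every hour for the remainder of the infusion and immediately (<30 minutes) after the infusion". For the analysis, Protocol 7.6.6.3 states: "Summaries of vital signs data over time and changes from Baseline over time will be provided".

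**The concern.** A baseline for a safety measure should be free of the drug's effect on the day it is taken. A rule based on the date alone achieves this only if everything measured on the dosing date is measured before dosing. Vital signs are deliberately measured after dosing starts as well, so taking the last value of the day takes a post-dose value.

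Safety is the primary objective, and vital signs are a named component of it. Protocol 7.2.1 describes infusion reactions that show as fever, tachycardia and lower blood pressure, all of which the scheduled vital signs measure. If the first infusion moves any of these, the movement is subtracted from that subject's later changes from Baseline. A real infusion effect could be masked, or an opposite change could appear. SAP 8.1 also presents naïve and IST subjects separately, so those vital-sign tables would consist entirely of subjects under this rule.

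**Working it through.** The plan states no figure to reproduce. The check applies the written rule to the written schedule.

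**Inputs**
- Infusion length: about 4 hours, or 240 minutes (Protocol 7.4.2).
- Minimum readings: one within 30 minutes before; at least every 30 minutes in the first hour; at least hourly thereafter; one within 30 minutes after (Protocol 7.5.2.4; vital-signs footnote of both schedules).
- Rule: last non-missing value dated on or before the first-dose date (SAP 5.1).

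**Day 1 readings, in minutes from the start of infusion**

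| Phase | Times | Count |
|---|---|---|
| Before | between −30 and 0 | 1 |
| During, first hour | 30, 60 | 2 |
| During, remainder | 120, 180, and possibly 240 | 2 or 3 |
| After | between 240 and 270 | 1 |

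The total is 1 + 2 + 2 + 1 = 6, or 1 + 2 + 3 + 1 = 7 if a separate 240-minute reading is taken. All carry the same date, and only one is pre-dose.

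**Applying the rule**
- As written, it selects the reading at 240 to 270 minutes, about 4 to 4.5 hours after dosing began. If that is missing, it selects the last reading during the infusion, which is still post-dose.
- Limited to readings before the infusion starts, it selects the single reading between −30 and 0 minutes.

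**Effect on change from Baseline**

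Let B be the pre-infusion value, d the shift present at the post-infusion reading, and Y a later reading.

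- Change from the pre-infusion baseline: Y − B.
- Change under the rule as written: Y − (B + d) = (Y − B) − d.

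The error is −d at each later time point for that subject. If m of N summarised subjects are naïve or IST, with mean shift D among them, the overall mean change is off by −(m/N) × D, and the naïve and IST tables by their own mean shift. The documents give neither d nor m. Purely as an assumed illustration, a heart-rate shift of +5 to +15 bpm gives an error of −5 to −15 bpm, and a temperature shift of +0.3 to +1.0 °C gives −0.3 to −1.0 °C.

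**The case against.** The strongest reply is that a pre-infusion value is plainly intended. Protocol 7.5.1 and footnote b of both schedules require same-day assessments to be finished before the infusion, and Protocol 7.5.2.4 puts vital signs ahead of the visit's other assessments. This does protect the other scheduled assessments. It cannot protect vital signs, because the same schedules order further readings during and after the infusion, and SAP 5.1 does not say which one counts.

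It is also fair that little hangs on the output. The summaries are descriptive, with no test or decision rule. Adverse events and typed infusion reactions are reported without using this baseline. Protocol 7.4.3 reports no drug-related infusion reactions at any dose to date in the Phase 1/2 study, so the shift may be small. This lowers the severity but does not make the selected reading the right one.

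A reader might infer more than the documents support:

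- **That SAP Table 7.3.1 repeats the error.** Its baseline window is also set by day, but the table covers 12-weekly assessments, and vital signs are taken every 2 weeks.
- **That the SAP's same-day tie-break forces the later reading.** The instruction to "use the time or the sequence number to select the later record" concerns termination and unscheduled visits mapped to post-baseline windows. It does not choose a baseline.
- **That the SAP contradicts the protocol's definition of a value taken immediately before treatment.** That definition is of pre-treatment baseline, which the protocol uses for efficacy. Safety changes are measured from study baseline, defined only as this study's baseline visit, with no time of day. The protocol leaves the same gap.
- **That desaturation would be masked.** Oxygen saturation is not among the vital signs in Protocol 7.5.2.4.
- **That the primary safety evaluation is compromised.** Adverse-event and infusion-reaction reporting stands independently.

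**Conclusion.** The point holds for vital signs in naïve and IST subjects. Applied literally, SAP 5.1 returns a reading taken after dosing began, and the planned changes from Baseline carry the first infusion's shift with its sign reversed. This is a stated rule that gives the wrong value, not merely a missing detail.

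Severity is minor to moderate. The affected output is descriptive, the number of naïve and IST subjects among the approximately 20 planned is not stated, and the size of the shift is unknown. The conclusion assumes that the rule is programmed as written and that the first dose falls on the day of the Baseline vital signs, as the schedules show. For IST subjects the first dose in this study is not their first exposure, so the problem is a post-infusion reading rather than a first-exposure effect. Rollover subjects fall outside the rule because their baseline comes from the feeder study.

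**What to change.** In SAP 5.1, add one sentence for naïve and IST subjects: *for vital signs, baseline is the last non-missing reading before the start of the first UX003 infusion in this study, using the planned pre-infusion time point*. Keep the words *in this study*, so that the IST baseline does not move back to the original start of UX003. Leave the separate uGAG baseline definitions as they are.

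The cost is one sentence and a small programming change, since the pre-infusion reading is already required. The change removes drug and reaction effects from the baseline but not necessarily premedication effects: antihistamine is given about 30 to 60 minutes before the infusion (Protocol 7.4.2.1), so a reading in the last 30 minutes may already reflect it.

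A further summary of the largest change within each infusion, measured from that day's pre-infusion reading, is optional and not part of the correction.

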#### **Definition of Terms**

Investigational Product is defined as, "A pharmaceutical form of an active ingredient or placebo being tested or used as a reference in a clinical trial, including a product with a marketing authorization when used or assembled (formulated or packaged) in a way different from the approved form, or when used for an unapproved indication, or when used to gain further information about an approved use" (from International Conference on Harmonisation of Technical Requirements for Registration of Pharmaceuticals for Human Use [ICH] Harmonised Tripartite Guideline E6: Guideline for Good Clinical Practice).

The terms "Investigational Product" and "study drug" may be used interchangeably in the protocol.

Primary (or feeder) study is defined as the Ultragenyx-sponsored study a subject completed immediately prior to enrollment in this long-term treatment and extension study. The terms "primary study" and "feeder study" may be used interchangeably in the protocol.

"Study baseline" is defined as the baseline visit of this long-term treatment and extension study (UX003-CL202).

"Pre-treatment baseline" is defined as the baseline visit in the primary study (e.g., UX003-CL301) or the visit and/or assessment performed just prior to treatment with UX003.

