# 7.5.2 Safety Assessments (Primary Objective)

For the purposes of this study, all safety assessments will be performed on all subjects entering from a prior study with UX003, unless otherwise specified. UX003-naïve subjects will be required to complete all applicable (age- and ability-appropriate) study assessments as indicated in Table 2.1.

Safety will be evaluated by the incidence, frequency and severity of AEs and SAEs, including clinically significant changes from study baseline to scheduled time points in vital

signs, weight, physical examination, clinical laboratory evaluations, and concomitant medications. Evaluation of valvular function and cardiac function by ECHO will be made primarily for safety purposes.

APRG reporting is a novel method synthesizing safety symptoms into multi-domain physiology related groups. APRG reporting has been incorporated into the study design to detect adverse physiologies that might be expressed variably within and between subjects in a study.

To assess the immune response to UX003, the development of any antibodies to rhGUS, and complement C3, C4, and CH50 levels will also be evaluated if a drug-related hypersensitivity reaction is suspected. Pregnancy testing (or pregnancy of partner, if needed) will also be conducted.

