# 7.5.2.5 Clinical Laboratory Tests for Safety

The clinical laboratory evaluations to be performed in this study are listed in Table 7.5.2.5.1.

Clinical laboratory testing will be performed at the Baseline visit and at 48-week intervals as indicated in the Schedule of Events (Table 2.1). Clinical laboratory tests performed at the primary (or feeder) study End of Treatment visit or within 30 days prior to Baseline may be used for the study baseline. Blood and urine samples will be collected prior to administration of study drug; fasting is not required. Refer to the Laboratory Manual for additional details.

Chemistry	Hematology	Urinalysis
Alanine aminotransferase (ALT)	Hematocrit	Appearance
Alkaline phosphatase	Hemoglobin	Color
Amylase	Mean corpuscular hemoglobin (MCH)	pН
Aspartate aminotransferase (AST))	MCH concentration (MCHC)	Specific gravity
Bilirubin (direct and total)	Mean corpuscular volume (MCV)	Ketones
Blood urea nitrogen (BUN)	Platelet count	Protein
Calcium	Red blood cell (RBC) count	Glucose
Chloride	Reticulocyte count	Bilirubin
Creatinine	Neutrophil count (absolute and %)	Nitrite
Gamma-glutamyl transpeptidase (GGT)	Lymphocyte count (absolute and %)	Urobilinogen
Glucose	Monocyte count (absolute and %)	Hemoglobin
Lactate dehydrogenase (LDH)	Eosinophil count (absolute and %)	Creatinine
Phosphorus	Basophil count (absolute and %)	
Potassium	White blood cell (WBC) count	
Protein (albumin and total)	WBC differential	
Sodium		

Subjects who experience a SAE possibly or probably related to study drug or other AE of concern may, at the discretion of the Investigator (and/or medical monitor), have additional blood samples taken for safety laboratory tests.

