#### 7.5.2.10 Adverse Events

For subjects enrolling from an Ultragenyx-sponsored clinical trial, all AEs will be recorded from the time the subject signs the informed consent for this extension study and completion of the End of Treatment visit in the primary study until 30 days after the last dose of study drug. Adverse events reported as ongoing at the primary study's End of Treatment visit and any new AEs prior to Baseline will be reviewed and recorded at Baseline visit. Any enrolling subject who had an early termination in the primary study will have their baseline AE information collected in the same manner as a subject who is treatment naïve or enrolling from a non-Ultragenyx sponsored study (see following paragraph).

For subjects who are treatment naïve or who are enrolling from a non-Ultragenyx sponsored clinical trial, all AEs will be recorded from the time the subject signs the informed consent until 30 days after the last dose of study drug.

The determination, evaluation, reporting, and follow-up of AEs will be performed as outlined in Section 8.5. At each visit subjects will be asked about any new or ongoing AEs since the previous visit. Assessments of AEs will occur at each study visit.

Clinically significant changes from study baseline in physical examination findings, vital signs, and clinical laboratory parameters, will be recorded as AEs or SAEs, if appropriate.

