4 STUDY CLINICAL OUTCOMES

4.1 Safety Assessments

Safety will be evaluated by the incidence, frequency and severity of AEs and serious adverse events (SAEs), including clinically significant changes from study baseline to scheduled time points in vital signs, weight, physical examination, clinical laboratory evaluations, and concomitant medications.

APRG safety reporting is a novel method that captures symptoms and their timing, allowing the diagnostic synthesis of infusion related events into one of several multi-domain physiology related groups to capture infusion-associated reaction (IAR) information. APRG reporting has been incorporated into the study design to detect adverse physiologies that might be expressed variably within and between subjects in a study.

To assess the immune response to UX003, the development of IgG antibodies to rhGUS, and complement C3, C4, and CH50 levels only be drawn if an IAR occurs will also be evaluated as indicated. Pregnancy testing (or pregnancy of partner, if needed) will also be conducted.

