8.8.2 Laboratory Parameters

Clinical laboratory values (in SI units) and changes from baseline at each assessment time point will be summarized for laboratory parameters in hematology, chemistry and urinalysis. The frequency and percentage of subjects who experience abnormal clinical laboratory results (i.e. outside of reference ranges) and/or clinically significant abnormalities after study drug administration will be presented by laboratory measurement.

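### For rollover subjects, SAP 5.1 takes the safety baseline from the feeder study, while SAP 4.1 and protocol 7.5.2 and 7.5.2.10 measure safety changes from the CL202 study baseline

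*SAP*

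**What the plan says.** The protocol's Definition of Terms separates two reference points. *Study baseline* "is defined as the baseline visit of this long-term treatment and extension study (UX003-CL202". *Pre-treatment baseline* is the baseline visit of the primary study, or the assessment just before UX003 treatment.

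For efficacy, protocol 7.6.5 uses pre-treatment baseline. For safety, which is the primary objective, protocol 7.5.2 evaluates adverse events "including clinically significant changes from study baseline to scheduled time points in vital" signs, weight, physical examination and laboratory tests. Protocol 7.5.2.10 has "Clinically significant changes from study baseline in physical examination findings, vital signs, and clinical laboratory parameters" recorded as adverse events where appropriate. SAP 4.1 uses the same reference: "clinically significant changes from study baseline to scheduled time points in vital signs, weight, physical examination, clinical laboratory evaluations".

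SAP 5.1 then sets the rule for rollover subjects: "The baseline (efficacy and safety) defined in feeder study will be used for this study". SAP 8.8.2 applies an unqualified baseline to the laboratory tables: "Clinical laboratory values (in SI units) and changes from baseline at each assessment time point will be summarized". SAP 9 reports no major change from Protocol Amendment 1.

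**The concern.** The SAP gives two incompatible instructions for the primary objective. SAP 4.1 starts safety change at entry to CL202; SAP 5.1 starts it, for rollovers, at the feeder-study baseline. Because SAP 8.8.2 does not say which baseline it means, a programmer would follow the definition in SAP 5.1.

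A laboratory change labelled with a CL202 visit would then include feeder-study time for rollovers. It would not share a time origin with the SAP's treatment-emergent adverse events (SAP 8.8.1) or exposure (SAP 5.8), both of which run from the first dose in CL202. SAP 8.1 also asks for an overall column beside the naïve, IST and rollover summaries. If the *other endpoints* rule in SAP 5.1 covers safety, naïve and IST subjects would enter that column from CL202 entry and rollovers from an earlier point.

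**Working it through.** The plan gives no figure to reproduce. The check is a comparison of texts, followed by simple arithmetic on elapsed time.

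**Which baseline each place uses for rollover safety**

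| Place | Reference point |
|---|---|
| Protocol 7.5.2 and 7.5.2.10 | Study baseline (CL202 visit) |
| SAP 4.1 | Study baseline |
| SAP 5.1 | Feeder-study baseline |
| Protocol 7.6.6, 7.6.6.2, 7.6.6.3; SAP 8.8.2 | Baseline, unqualified |

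The unqualified passages do not support the feeder reference. Protocol 7.6.6.3 says only "Summaries of vital signs data over time and changes from Baseline over time will be provided"; the capital letter suggests the CL202 visit but is not the defined term. Protocol 7.5.2.3 and 7.5.2.5 point the same way as 7.5.2: they let a physical examination or laboratory test from the feeder End of Treatment visit serve as the study baseline, so safety follow-up in CL202 starts where the feeder study ends.

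**Version lag does not explain it.** The SAP was written against Amendment 1 and the protocol is now at Amendment 3. The summaries of Amendments 2 and 3 list no change to the safety baseline, and SAP 4.1 already says study baseline, so the conflict exists inside the SAP.

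**Elapsed time**

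Inputs:
- The CL202 Baseline visit coincides with CL301 Week 48 (protocol 7.5.1 and Table 2.1, footnote a).
- CL301 Week 0 is the Randomization visit (protocol 7.5.4.10).
- Laboratory schedule: "Clinical laboratory testing will be performed at the Baseline visit and at 48-week intervals", that is, CL202 Weeks 48, 96 and 144 (Table 2.1).
- The CL301 safety baseline is assumed to be Week 0. The documents do not give the CL301 rule or the length of other feeder studies; 24 and 36 weeks are illustrative.

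With F the feeder weeks before the CL202 baseline and T the CL202 week, span = F + T and feeder share = F / (F + T).

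| F | T = 48 | T = 96 | T = 144 |
|---|---|---|---|
| 48 | 96 weeks, 48/96 = 50% | 144 weeks, 48/144 = 33% | 192 weeks, 48/192 = 25% |
| 36 | 84 weeks, 36/84 = 43% | 132 weeks, 36/132 = 27% | 180 weeks, 36/180 = 20% |
| 24 | 72 weeks, 24/72 = 33% | 120 weeks, 24/120 = 20% | 168 weeks, 24/168 = 14% |

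From study baseline the spans would be 48, 96 and 144 weeks. For CL301 rollovers the gap between the two references is 0 to about 48 weeks for any on-study CL301 baseline, and slightly more for a screening value. If vital-sign changes were tabulated at CL202 Week 12, F = 48 gives 48 + 12 = 60 weeks, of which 48/60 = 80% is feeder time.

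In the overall column, a Week 48 laboratory change could thus combine spans of about 48 weeks (naïve and IST) and 96 weeks (CL301 rollovers), on the same assumptions.

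**The case against.** The strongest reply is that the study-baseline passages concern adverse event assessment rather than tables. Protocol 7.5.2 and SAP 4.1 place these changes within the evaluation of adverse events, and protocol 7.5.2.10 concerns what is recorded as an event. None of the protocol's statistical passages uses the defined term for safety, and protocol 7.6.6.2 asks for laboratory statistics at baseline and each time point, not for change. This stands in part: a reader might infer that the protocol's statistical section prescribes study baseline for every safety change table, and it does not. But it does not prescribe the feeder baseline either. The only explicit safety reference in the protocol, and in the SAP outside 5.1, is study baseline.

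A second reply is that the feeder baseline looks deliberate, since SAP 5.1 names safety, and that it is reasonable: a rollover's CL202 baseline is generally an on-drug value, and long-term safety invites a cumulative view. That view is useful and worth keeping. But the SAP does not apply it consistently, because adverse events and exposure run from the first CL202 dose, and SAP 9 does not declare the choice.

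Third, the figures above measure elapsed time, not a changed result. That is correct. Vital-sign tables are also uncertain, since SAP 8.8.3 promises only summaries as appropriate.

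**Conclusion.** The contradiction is real and rests on the text alone: SAP 5.1 conflicts with SAP 4.1 and with protocol 7.5.2 and 7.5.2.10, and is not declared. It affects rollover laboratory change-from-baseline tables, any safety shift tables, and vital-sign changes where tabulated. Its size, about 48 extra weeks for CL301 rollovers, rests on the assumed Week 0 baseline. Mixing in the overall column further assumes that *other endpoints* in SAP 5.1 includes safety. It should be corrected, but it does not undermine the study.

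A reader might infer that the primary safety results are wrong. The documents do not support that. Treatment-emergent adverse event incidence is tied to the first CL202 dose, and observed values, abnormality frequencies and listings do not depend on the baseline chosen. The uGAG model is not touched, and the feeder baseline for rollover efficacy agrees with the protocol. A reader might also extend the point to the IST baseline rule. For safety, that rule, if it applies, starts at CL202 entry and so does not share the conflict. For efficacy it is a separate and probably small matter, because protocol 7.5.4 generally limits those assessments to ones done in the feeder study, which the protocol defines as Ultragenyx-sponsored.

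**What to change.** In SAP 5.1:

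- Limit the feeder-study baseline to rollover efficacy.
- Use the CL202 study baseline for safety change and shift summaries in all cohorts, taking CL301 Week 48 data where protocol 7.5.1 allows.
- Show rollover safety change from the feeder baseline as a separate display, labelled as cumulative.

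If the sponsor prefers the feeder baseline as the main display, it should reconcile SAP 4.1 with SAP 5.1, declare the departure in SAP 9, and still show change from study baseline.

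The cost is SAP wording, one extra baseline variable and slightly longer tables. No new data are needed: Table 2.1, footnote a, already requires any listed assessment missed at the feeder final visit to be done before the first CL202 infusion.
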